# Medication Error

A medication error is an unintended failure in the drug treatment process that leads to, or has the potential to harm the patient (EMA Good Practice Guide definition).

- A 'failure in the drug treatment process' does not refer to lack of efficacy of the drug, rather to human or process mediated failures.
- The error is unintended. The concepts of intentional overdose, off-label use, misuse and abuse as defined in GVP (good pharmacovigilance practices) Module VI.A.2.1.2 are outside scope and should be clearly distinguished from medication errors.
- 'Drug treatment process' includes prescribing, storing, dispensing, preparation for administration and administration of a medicine in clinical practice.

The dose and administration of the study medication is described in section 6 Study Treatment. Any deviation from the study medication (wrong medication, wrong dose, wrong route of administration, wrong patient) is a medication error. Any higher administered dose of the study medication, than described in section 6 Study Treatment, is an overdose.

#### 9.3.2 Recording Adverse Events

All AEs, serious and non-serious, that occur during the period of observation defined for the clinical study (section III, Flowchart of Study) have to be fully documented in the eCRF according to the provisions given in this section of the study protocol and eCRF completion guidelines, as well as in the subject's source data. This applies also to AEs in subjects who signed the informed consent but never received the study drug. AEs considered not related to study medication observed after Day 36 (defined closing visit) will not be recorded in the eCRF.

In addition, for a subset of AEs (SAE, AESI, AE leading to withdrawal) immediate reporting from investigator to sponsor is required (Immediately Reportable Adverse Events, IRAE). This is further detailed in Appendix 2. The following information is necessary:

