# Closing Visit Day 36 (+35, up to Day 71 if required):

All subjects treated with IMP will attend a closing visit including the final safety examination, and a safety follow-up at least 5 weeks after the surgery, scheduled on Day 36 (+35, up to Day 71 if required).

Using a phone call instead of a protocol-directed in-person study visit is acceptable if all tests and procedures scheduled for Day 36 (+35) requiring an in-person visit (physical examination, vital signs, samples for laboratory tests), were performed on the day of hospital discharge. These results are to be entered in the eCRF in the fields provided for the closing visit.

The documentation of transfusion products, concomitant medication or treatment, and the recording of AEs can be performed by using a phone call. In addition, the follow-up of AEs can be completed with the subject by telephone (for the follow-up of AEs please refer to section 9.3.4).

An appropriate documentation of the phone call is kept.

The following procedures will be performed:

- A physical examination will be performed.
- **Vital signs** (including pulse [heart rate], blood pressure, respiratory rate, body temperature) will be recorded.
- Sample for **coagulation activation tests** (PT(INR), aPTT, TAT, F1+2, D-dimer, PS, PC, AT III, TT, TGT) will be taken.
- Samples for **clinical laboratory parameters** (hematology, clinical chemistry, urinalysis) will be taken:
  - **Hematology** (RBC, WBC, platelet count, hemoglobin, hematocrit)
  - Clinical chemistry (ASAT, ALAT, creatinine, creatinine clearance, BUN/Urea, γ-GT, AP, total bilirubin, potassium, sodium, calcium, chloride)
  - **Urinalysis** (pH, blood, WBC, protein, glucose, ketone bodies, nitrite, bilirubin, urobilinogen)
- Retention samples for viral safety laboratory parameters will be taken.
- Samples for virus serology laboratory parameters (hepatitis B, hepatitis C, HIV) will be taken.
- **Transfusion products** (allogenic blood products) will be documented.
- **Concomitant medication or treatment**: type of concomitant medication/treatment, dose/schedule, duration, and the indication the concomitant medication/treatment was given for will be documented continuously up to Day 36 (+35).
- **AEs** will be recorded continuously up to Day 36 (+35).

Further details on the visit schedule that will be used for the assessment of the efficacy and safety parameters in this study are presented in section III, Flowchart of Study.

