#### Individual Subject

Regular duration of individual study participation for eligible screened subjects is at least 5 weeks plus time between screening (signed ICF) and surgery.

Each subject fulfilling the intra-operative inclusion criteria will be administered BT524 or cryoprecipitate during surgery. The usual stay in hospital after elective surgery varies depending on the type of surgery and subjects overall conditions. Each subject will have follow-up visits 1, 2, 4 and 7 days after surgery (Day 2, 3, 5 and 8) and the day of discharge from hospital will be recorded.

Subsequent, each subject has to attend a closing visit including the final safety examination, and a safety follow-up at least 5 weeks after surgery, scheduled on Day 36. Using a phone call for the closing visit Day 36 is acceptable if all tests and procedures scheduled for Day 36 requiring an in-person visit, were performed on the day of hospital discharge.

The closing visit can be postponed up to Day 71 (Day 36 +35) if required due to subject's availability (e.g., stay in rehabilitation center).

Subjects not meeting inclusion criteria or meeting exclusion criteria are screen failures and will end study participation at the day of screen failure. Subjects that do not meet the intra-operatively inclusion criterion are also considered as screen failure and will end study participation on the day of the surgery.

A subject is considered to have completed the study when he/she is presumed to have followed the protocol (i.e., completed visits approximately 5 weeks after surgery). If for any reason, a subject discontinues involvement in the study early, every effort should be made to ensure the subject attends a closing visit (section 4.4).

For each subject date and reason for the end of the study participation will be recorded.

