# 9.3.3 Period of Observation

The period of observation for collection of AEs extends from the time the subject signs the ICF until the last study visit (Day 36), which is scheduled 5 weeks after the day of the surgery (day of IMP administration).

Abnormal, clinically relevant findings or observations made prior to signature of informed consent are to be recorded as medical history/concomitant disease but not as AEs.

AEs (including any change in severity or trait of the concomitant disease/ medical history) occurring in the pre-treatment period between signature of informed consent until first administration of study medication are non-treatment emergent AEs (NTEAEs).

AEs (including any change in severity or trait of the concomitant disease/ medical history) occurring from the administration of study medication until the subject's last study visit are treatment-emergent AEs (TEAEs).

If an SAE occurs in a subject after the period of observation, i.e., after the last study visit, which is considered by the investigator to be related to the study medication, this should be recorded as SAE and follow the immediate reporting process for SAEs as described

in Appendix 2. If the eCRF has been closed for the subject, the investigator should contact the sponsor to determine how to report the SAE (see also section 7.4).

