## 10.7 Safety Analysis

AEs will be coded using the most current version of Medical Dictionary for Regulatory Activities (MedDRA®). The version used will be defined in the SAP. Incidence rates (i.e., number and percentage of affected subjects) will be calculated for the coding levels *SOC* and *preferred term* and will be presented by treatment arm. Further analyses of AEs will focus on seriousness, intensity, causal relationship to IMP, and outcome. IRAE including SAEs etc. will be displayed in detail.

Safety laboratory assessments (hematology, clinical chemistry, urinalysis and coagulation parameters) will be categorized with respect to the laboratory specific reference ranges as normal/abnormal. Abnormal values will be further classified with respect to clinical relevance. Changes over time will be described by means of "shift-tables" by treatment arm as well as summarized with descriptive statistics by time point and treatment arm.

Vital signs data will be summarized descriptively before and after surgery by treatment arm.

The frequency of thrombosis and of TEEs, virus status, exposure data and concomitant medication will be summarized by treatment arm.

All safety analyses will be based on the SAF.

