12.6.1 Adverse Events

Adverse events will be coded using the most updated version of the MedDRA® dictionary.

Adverse events occurring during or after the administration of study medication are TEAEs. If a partially missing AE start date is imputed, the imputed date will be used to assess if the AE is treatment emergent. If AE start date is completely missing and AE end date/time is after IMP start date/time or if it is completely missing, then it is a TEAE. All other AEs are regarded non-treatment emergent.

The search criteria for the adverse events of special interest are specified in the table below:

AESI	Search Criteria
Thrombosis or TEE	SMQ: Embolic and thrombotic events (narrow)
Relevant bleeding complication	All AESIs ticked as AESI, but not falling under categories "Thrombosis or TEE" or "Suspicion of transmission of infective agents (viral safety)"
Suspicion of transmission of infective agents (viral safety)	Preferred terms: "transmission of infectious agent via product" and "suspected transmission of infectious agent via product"

Adverse events related to Hypersensitivity/anaphylactic reactions/anaphylactic shock will be selected by using the following criteria: SMQ: Hypersensitivity, (narrow), Anaphylactic reaction (narrow), and Anaphylactic shock conditions (narrow).

Adverse events related to bleeding related ischaemic events will be selected by using the following criteria: SMQ: Ischaemic heart disease: Myocardial infarction (narrow), Other ischaemic heart disease (narrow); Ischaemic colitis (broad); Ischaemic central nervous system vascular conditions (narrow); Embolic and thrombotic events, arterial (narrow); Embolic and thrombotic events, venous (narrow); PT: Peripheral ischaemia; Ischaemia; Gastric ischaemia; Hepatic ischaemia; Ischaemic contracture of the left ventricle; Dry gangrene; Ischaemic gastritis; Ischaemic limb pain; Necrosis ischaemic; Spleen ischaemia; Uterine ischaemia.

If a serious adverse event (SAE) occurs in a subject after the period of observation, i.e., after the last study visit, and is considered by the investigator to be related to the study medication, this should still be recorded as a SAE. If the eCRF has been closed for the subject, the investigator should contact the sponsor to determine how to report the SAE.

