The total number and percentage of subjects reporting at least one AE and the absolute count of AEs will be tabulated for each treatment, treatment arm and overall once for the overall trial population and separately by type of surgery (spinal and abdominal surgery), sex and race. The initial summary will also provide a breakdown of the following:

- Any AE
- Any non-severe AE
- Any TEAE
- Any NTEAE
- Any non-serious TEAE
- Any non-severe TEAE
- Any treatment-related TEAE
- Any severe AE
- Any severe TEAE
- Any severe treatment-related TEAE
- Any SAE
- Any serious TEAE
- Any serious treatment-related TEAE
- Any AESI
- Any treatment-emergent AESI
- Any treatment-emergent treatment-related AESI
- Any AE leading to discontinuation from study
- Any TEAE leading to discontinuation from study

- Any treatment-related TEAE leading to discontinuation from study
- Any AE with outcome of death
- Any TEAE with outcome of death
- Any treatment-related TEAE with outcome of death
- Any TEAE of special interest
 - Thrombosis or TEE
 - Suspicion of transmission of infective agents
 - Relevant bleeding complication
- Any TEAE of Hypersensitivity/ anaphylactic reactions/ anaphylactic shock
- Any TEAE of Bleeding related ischaemic events

The number of events, number and percentage of subjects reporting AEs will be tabulated (as well for causality and maximum severity) in the following way once for the overall population, and separately by type of surgery (spinal and abdominal surgery) and sex in the following:

- Treatment-emergent AEs by system organ class and preferred term
- Serious treatment-emergent AEs by system organ class and preferred term
- Causally related TEAE by system organ class, preferred term and maximum severity
- Not Causally related TEAE by system organ class, preferred term and maximum severity
- Causally related Serious TEAE by system organ class, preferred term and maximum severity
- Not Causally related Serious TEAE by system organ class, preferred term and maximum severity

The number of events, number and percentage of subjects reporting AEs will be tabulated (as well for causality and maximum severity) in the following way once for the overall population, and separately by type of surgery (spinal and abdominal surgery) in the following:

- Non-treatment emergent AEs by system organ class and preferred term (will not be tabulated for maximum severity or causality)

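### Protocol 9.3.2 leaves unrelated adverse events after Day 36 out of the eCRF, while 7.1 and 9.3.3 include events up to a closing visit that may be as late as Day 71

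*Protocol*

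**What the plan says.** **Recording.** Protocol 7.1, under the closing visit, says that AEs "will be recorded continuously up to Day 36 (+35"), with no condition on causality. The Flowchart marks adverse events in its last column, which carries the same +35 window. Section 9.3.2 opens by requiring every AE in the observation period to be documented, and refers to the Flowchart for that period. It then adds: "AEs considered not related to study medication observed after Day 36 (defined closing visit) will not be recorded in the eCRF".

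**Length of the period.** Section 7.2 allows the late visit: "The closing visit can be postponed up to Day 71 (Day 36 +35) if required due to subject's availability". Section 9.3.3 runs AE collection from consent "until the last study visit (Day 36), which is scheduled 5 weeks after the day of the surgery", without mentioning the window. The same section defines treatment-emergence by the subject's own last visit: AEs "occurring from the administration of study medication until the subject's last study visit are treatment-emergent AEs (TEAEs").

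**Analysis.** SAP 12.6.1 gives a start but no end: "Adverse events occurring during or after the administration of study medication are TEAEs". The summaries are crude. Protocol 10.7 says "Incidence rates (i.e., number and percentage of affected subjects) will be calculated", and SAP 12.6.1 says "The total number and percentage of subjects reporting at least one AE and the absolute count of AEs will be tabulated". Neither sets a common cut-off or adjusts for length of observation.

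**The concern.** Two people who both follow the protocol could treat the same event differently. If the closing visit is postponed, 7.1 has an unrelated late event entered and 9.3.2 keeps it out. On the literal reading of 9.3.2, a causality opinion decides whether the event is in the analysis data at all, when it should only decide how the event is labelled. An all-causality TEAE table would then hold all events up to Day 36 and a causality-selected set afterwards.

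The second issue remains even if recording is complete. A subject whose closing visit is on Day 71 has twice as long to accumulate events as one who closes on Day 36, and the percentages treat them alike. The protocol's Introduction expects BT524 to show a safety advantage over standard treatment, so the AE tables carry weight in the benefit-risk case.

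**Working it through.** **1. The window.** The latest closing visit is Day 36 + 35 = Day 71, as stated in 7.2. Surgery is Day 1, so the observation time after surgery is 36 − 1 = 35 days at the shortest and 71 − 1 = 70 days at the longest. The ratio is 70/35 = 2.

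**2. One event under each rule.** Take an AE judged unrelated, with onset on Day 50, in a subject whose closing visit is on Day 60 (days chosen for illustration).

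| Source | Result |
|---|---|
| 7.1 closing visit | Recorded |
| 9.3.2 opening sentence, with the Flowchart | Recorded |
| 9.3.2 sentence on unrelated AEs | Not recorded in the eCRF |
| 9.3.3 treatment-emergence | Counts as a TEAE |
| Appendix 2, if the event is an SAE or AESI | Recorded on the eCRF AE page |

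**3. Which events are exposed.** Section 9.3.1 lists thrombosis or TEE, relevant bleeding complications and suspected transmission of infective agents as AESIs. It makes all SAEs, all AESIs and all AEs leading to withdrawal immediately reportable, with no causality condition. Appendix 2 requires each immediately reportable event to be on the eCRF AE page as well as on the report form. What 9.3.2 clearly removes is therefore the remainder: unrelated, non-serious, non-AESI events with onset from Day 37 to a postponed closing visit. For late unrelated SAEs and AESIs, 9.3.2 and Appendix 2 give opposite instructions, because 9.3.2 states no exception.

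**4. Size of the window effect.** The documents give no AE rates, so all rates here are assumptions. Let p be the 35-day incidence and r the share of later events that is recorded. With a constant hazard, the recorded incidence to Day 71 is

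P = 1 − (1 − p)^(1 + r).

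If instead the hazard halves every L days and all events are recorded, the exponent becomes 1 + 2^(−35/L). This is 1.031 for L = 7 and 1.177 for L = 14.

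| p | r = 0 | r = 0.10 | r = 0.25 | r = 0.50 | r = 1 | Falling hazard, all recorded (L = 7 to 14) |
|---|---|---|---|---|---|---|
| 5% | 5.0% | 5.5% | 6.2% | 7.4% | 9.75% | 5.2% to 5.9% |
| 10% | 10.0% | 10.9% | 12.3% | 14.6% | 19.0% | 10.3% to 11.7% |
| 20% | 20.0% | 21.8% | 24.3% | 28.4% | 36.0% | 20.6% to 23.1% |

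For example, with p = 0.10 and r = 0.25, P = 1 − 0.90^1.25 = 12.3%.

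These figures apply to a subject followed to Day 71. If a fraction f of an arm closes then and the rest on Day 36, the arm's percentage moves by f × (P − p). With p = 10%, full recording and an assumed f of 0.10 to 0.50, the shift is 0.10 × 9.0 = 0.9 to 0.50 × 9.0 = 4.5 percentage points under a constant hazard. Under the falling hazard it is 0.10 × 0.30 = 0.03 to 0.50 × 1.66 = 0.83 points.

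**The case against.** The strongest reply is that Day 36 in 9.3.2 is only a visit label. The sentence itself calls it the defined closing visit, 9.3.3 uses Day 36 in the same way, and the opening of 9.3.2 points to a Flowchart whose last column includes the window. On that reading only unrelated events after the actual closing visit are dropped, and the recording conflict disappears. The reading is sensible and may be what was meant, but the text does not say so, and the literal reading is equally open to a site. It also leaves the unequal windows in place.

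Three stronger conclusions are tempting, and the documents do not support them.

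- *Late thromboses would be lost.* Appendix 2 gives AESIs and SAEs a route to the eCRF that does not depend on causality. What stands is that 9.3.2 should not contradict that route.
- *The TEAE period has no end.* Protocol 9.3.3 ends it at the last study visit, and SAP section 4.0 says the SAP is to be read with the protocol. What stands is that SAP 12.6.1 omits the end while noting that related SAEs after the last visit are still recorded. Taken alone, its definition would count those as TEAEs.
- *The arms would be biased against each other.* Sections 9.3.2 and 9.3.4 give causality to the investigator. Nothing says that the unblinded anaesthesiologist judges events after Day 36. Postponement is for the subject's availability under one rule for both arms. Blinding is specified only for the surgery, so a difference is possible, but none is shown.

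It is also fair to say that safety is summarised descriptively, that crude percentages are conventional, and that the AE listings already show time to onset.

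**Conclusion.** The point holds as an inconsistency of limited reach. On its literal wording, 9.3.2 conflicts with 7.1, with the treatment-emergence definition in 9.3.3 and, for late unrelated SAEs and AESIs, with Appendix 2. The events clearly lost are unrelated, non-serious, non-AESI events between Day 37 and a postponed closing visit.

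Observation after surgery runs from 35 to 70 days. That twofold ratio describes the window and is not an effect on incidence. If events cluster soon after surgery, as the falling-hazard rows assume, the effect on percentages is small; only a roughly constant hazard makes it large. The main effect would be on absolute incidence.

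The number of subjects closing late is not in the documents. The protocol supplied is the UK version for PMP surgery at one site, so the recording conflict is shown for that version only. The SAP covers both types of surgery and describes the same closing window, so the point about crude percentages applies to the whole study.

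**What to change.** In Protocol 9.3.2, replace the reference to Day 36 with the subject's actual closing visit, so that every AE up to that visit is recorded regardless of causality. Align the end of the observation period in 9.3.3, and make clear in 9.3.2 and Appendix 2 that SAEs and AESIs are always entered in the eCRF. In SAP 12.6.1, state that the treatment-emergent period ends at the subject's last study visit. Add a TEAE and AESI summary restricted to onset up to Day 36 in both arms, with later events shown separately.

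The cost is wording, a few more AEs to record, and one additional table. The table needs only the onset dates that the eCRF already collects, and the SAP may be updated until database lock. For subjects whose participation has already ended, the study report should say which recording rule was followed.

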# • Diagnosis vs. Signs/Symptoms

The investigator should provide a diagnosis rather than individual signs and symptoms, wherever possible and appropriate. However, if there is not enough information to provide a diagnosis, individual signs and symptoms are to be recorded. If a diagnosis is accompanied by unusual symptoms, the diagnosis itself and the unusual symptoms have to be reported separately. For serious and other IRAEs the investigator shall provide any other supporting information that may be required for the assessment of the events.

A complication of an AE constitutes another AE. For example in diarrhea leading to dehydration, diarrhea and dehydration would be captured as separate AEs.

The eCRF provides for a number of items to be completed for each AE. This includes the onset date, end date, intensity/severity, seriousness, action taken with

study medication, treatment for the AE, outcome, and causal relationship of the AE with the study medication, other drugs, or study procedures (Appendix 2: Reporting Procedures).

**Severe vs. Serious:** The severity is used to describe the intensity of an event. This is not the same as seriousness, which is based on subject/event outcome or action criteria usually associated with events that pose a threat to subject's life or functioning. Seriousness, not severity, serves as the guide for defining regulatory reporting obligations.

# • Causal Relationship of AE

The causal relationship with the study medication has to be reported for each AE. It refers to the presence or absence of a reasonable possibility of a causal relationship between the study medication and the AE.

The investigator is asked to use medical judgment and take into account the nature of the AE, subject's medical and surgical history, temporal relation, response to withdrawal or interruption of study drug (dechallenge), response to re-introduction of study drug (rechallenge), any alternative explanations such as underlying or concomitant diseases, concomitant drugs, study procedures.

The investigator should also provide the causality assessment with the NIMP (e.g. background medication, concomitant medication - see Appendix 1 for definition).

The following categories are used:

- Related: There is a reasonable possibility of a causal relationship between the study medication and the AE.
- Not related: There is no reasonable possibility of a causal relationship between the study medication and the AE.

For serious and other immediately reportable AEs the investigator is asked to specify if there are alternative and/or additional explanations for the occurrence of the event, e.g. concomitant drugs, study procedures, or concomitant/underlying disease and should provide this information already with the initial case report.

